11.7 Exploratory Efficacy Analyses

The exploratory endpoints depend on data collected in an e-diary under the same constraints as the primary and secondary endpoints with response entry in the correct order and at the expected scheduled assessment times.

11.7.1 Headache Pain-Free

The endpoint of headache pain-free will be summarized at the 0.5, 1, 1.5, 3, 4, 24, and 48-hour post-dose time points. This summary will be presented by treatment group for the ITT, mITT, and PP populations, based on first dose.

Subjects who had a mild, moderate, or severe headache at the time of dosing will be the reference subjects for this summary. Subjects missing a headache severity at baseline will not be summarized. Subjects missing a severity assessment at a post-dose time point will not be counted as pain-free.

11.7.2 Sustained Headache Pain-Free

Sustained pain-free response will also be summarized at the 24 and 48-hour post-dose time points. This summary will be presented by treatment group for the ITT population, based on first dose.

Sustained Pain-Free is defined as experiencing headache pain-free at two hours after first dose and at the subsequent indicated assessment time, having not used any medications after the first dose.

11.7.3 MBS-Free

The endpoint of MBS-free will be summarized at the 0.5, 1, 1.5, 3, 4, 24, and 48-hour post-dose time points. This summary will be presented by treatment group for the ITT, mITT, and PP populations, based on first dose. This summary will be repeated separately for each symptom (nausea, phonophobia, and photophobia) on the ITT population.

Subjects missing symptoms at baseline or at the summarized time point will not be summarized at that time point.

11.7.4 Presence of Migraine Symptoms

Counts and percentages of the presence of migraine symptoms will be presented at the 0.5, 1, 1.5, 2, 3, 4, 24, and 48-hour post-dose time points. This will be summarized based on the first dose using the ITT population, and based on the second dose for recurrence and rescue using the ITT-2nd Dose population.

The presence of the following symptoms will be presented based on the response to the presence of that symptom at that time point.

- Nausea
- Phonophobia
- Photophobia
- Vomiting

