### 5.6.3 Treatment

Subjects will be allowed up to 8 weeks to treat an acute migraine attack of moderate or severe intensity that is not improving. The attack is to be treated within 4 hours of onset.

- **Prior to dosing the subject will record:**
  - Time of onset
  - Time migraine pain becomes moderate or severe and the severity ((2) moderate or (3) severe) of the pain.
  - Presence or absence (yes or no) of each of the following associated symptoms of migraine: nausea, phonophobia and photophobia.
    - From the list of associated symptoms **present** the subject will identify which **ONE** is most bothersome to them as the MBS.
  - Presence or absence (yes or no) of vomiting.
  - Degree of interference with normal activities
- **Subject will dose with study drug and record time of dosing.**
- Subject will record their response to treatment for 48 hours after dosing with study drug. Total time to record response is up to 72 hours (See [Section 9.1.8](#)).
- Subjects will be asked about any adverse events (if they are feeling anything unusual) and about the use of any concomitant medications.

### 5.6.4 End of Study/Visit 2

The following assessments will be performed:

- Collect any unused study drug and review dosing compliance.
- Collect resource utilization (See [Section 9.1.1.3](#)).
- Collect information on missed days of work and/or school due to migraine.
- Have subject complete C-SSRS (See [Section 9.1.6](#) and [Appendix 5](#)).
- Review any information reported since **Visit 1** regarding AEs and use of concomitant medication and confirm/assess for AEs and use of concomitant medications not already reported.
- Perform a brief symptom-related physical examination if indicated by an AE (See [Section 9.1.2](#)).
- Obtain vital sign readings (See [Section 9.1.3](#)).
- Perform a 12-lead ECG (See [Section 9.1.4](#)).
- Collect blood and urine samples for clinical laboratory tests (hematology, chemistry, and urinalysis) (See [Section 9.1.5](#)). The laboratory tests will include a urine pregnancy test for WOCBP. A positive urine pregnancy test will be confirmed with a serum  $\beta$ HCG test. (The confirmatory test may be run in the local clinical laboratory).
- Subject's participation in study is complete.

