##### **10.5.4.4 Associated Symptoms of Migraine**

Descriptive analysis of the associated symptoms of migraine, nausea, phonophobia and photophobia, will be performed at 2 hours. Freedom from each symptom will be defined as a 'no' response to the presence of the symptom 2 hours after dosing with study drug.

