3.3 Exploratory Efficacy Endpoints

- Headache pain-free at 0.5, 1, 1.5, 3, 4, 24, and 48 hours post-dose based on first dose
- Sustained headache pain-free at 24 and 48 hours post-dose based on first dose
- MBS-free at 0.5, 1, 1.5, 3, 4, 24, and 48 hours post-dose based on first dose
- Presence of migraine symptoms (nausea, phonophobia, photophobia, vomiting) at all-time points based on first and second dose
- Headache relief at all time points based on first dose
- MBS-free at 0.5, 1, 1.5, 2, 3, 4, 24, and 48 hours post-dose by chosen MBS based on first dose
- Time to headache pain-free through 24 hours after first dose
- Time to headache relief through 24 hours after first dose
- Time to MBS-free through 24 hours after first dose, overall and separately for each symptom
- Disability at all time points based on elapsed times since first and second doses
- Incidence of rescue or recurrence medication use at 2 hours, between 2 and 24 hours, and between 24 and 48 hours post first dose
- Incidence of headache recurrence
- Patient global impression of change (PGIC) scale at two hours post-dose, based on elapsed times since first and second dose
- Headache pain-free after a second dose, separately for rescue and recurrence, at all time points
- Time to headache pain-free through 24 hours after a second dose, separately for rescue and recurrence

- Headache relief after a second dose, separately for rescue and recurrence, at all time points
- Time to headache relief through 24 hours after a second dose, separately for rescue and recurrence
- MBS-free after a second dose, separately for rescue and recurrence, at all time points, overall and separately for each symptom
- Time to MBS-free through 24 hours after a second dose, separately for rescue and recurrence, overall and separately for each symptom

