5 GENERAL SPECIFICATIONS

This section details the specifications for summarizing all efficacy and safety endpoints.

Continuous variables will be summarized using descriptive statistics, i.e. n (number of subjects with available data), mean, median, standard deviation, minimum, and maximum. For those measures that are analyzed using change from baseline scores, descriptive statistics will also be presented on observed scores, unless otherwise noted.

Minimum and maximum values will be presented to the same precision as the raw data. Mean and median will be presented to one more decimal place than the raw data. Standard deviation will be

presented to two more decimal places than the raw data. P-values will be presented to three decimal places.

Categorical variables will be summarized using counts and percentages. Unless otherwise specified, percentages will be calculated using the numbers of subjects in the summarized population in each treatment group as denominators. Percentages will be presented with a precision of 1 digit after the decimal.

In this study, subject will enter the efficacy data on dosing and post-dose assessments in an e-diary. The e-diary records the date and time of the first dose and of the second dose and is programmed to assess specific time points and assessments as defined in the protocol based on the timing of the dose as recorded. This data is collected in the e-diary when e-diary is in migraine mode. Specifics of Migraine Mode are as below:

- Migraine Mode – First Dose
 - The e-diary enters Migraine Mode **ONLY** if the subject indicates taking his/her first dose of study medication
 - Post Dose Assessments will be completed using the Migraine Questions button at specific time intervals for up to 48 hours after the subject confirms taking study medication

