11 EFFICACY ANALYSES

This section details the specifications for summarizing efficacy endpoints.

The primary and key secondary efficacy analyses will be performed on the ITT, mITT, and PP populations. The primary analysis population is the mITT population. Exploratory efficacy analyses will be performed on the ITT and ITT-2nd Dose populations, depending on the endpoint. Efficacy responses will also be presented in a listing.

Unless otherwise stated, all primary, secondary, and exploratory efficacy hypotheses will be tested using a logistic regression model with treatment group and background use of medication to reduce the frequency of migraine episodes as covariates. For treatment comparisons, an estimate of the odds ratio of achieving a response, as well as the corresponding confidence interval and p-value using Wald's test, will be computed. Tests of the primary and key secondary endpoints will be conducted at a one-sided significance level of 0.025; tests of all other endpoints will be conducted at a two-sided significance level of 0.05.

Analyses of second-dose endpoints with too few subjects in the treatment-sequence-subpopulation groups may have too little data separation for a logistic regression model to reach a stable solution. For these models, the "Firth" modification of the maximum likelihood estimation will be used to achieve a solution.

The efficacy endpoints will depend on data collected by e-diary that depends on subject's response entry in the correct order and at the expected scheduled e-diary assessment times. Assessment times are analyzed as calculated by the e-diary and not as part of analysis programming.

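### The individual-symptom summaries ignore whether the symptom was present before dosing, so never-affected subjects count as free of it and resolution is mixed with new onset

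*SAP*

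**What the plan says.** **The rule.** SAP 11.7.4 gives counts and percentages of each symptom at every post-dose time point: "The presence of the following symptoms will be presented based on the response to the presence of that symptom at that time point". On the analysis set it says: "This will be summarized based on the first dose using the ITT population". The ITT-2nd Dose population is used after a second dose. SAP 5 sets the default denominator: "percentages will be calculated using the numbers of subjects in the summarized population in each treatment group as denominators".

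**The protocol's version.** Section 10.5.4.4 covers nausea, phonophobia and photophobia, but not vomiting: "Freedom from each symptom will be defined as a 'no' response to the presence of the symptom 2 hours after dosing with study drug". No positive answer before dosing is required.

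**What is collected.** Protocol 5.6.3 has the subject record, before dosing: "Presence or absence (yes or no) of each of the following associated symptoms of migraine: nausea, phonophobia and photophobia". Vomiting is recorded then too. SAP 8.5 tabulates these baseline answers by treatment group but does not link them to the post-dose percentages.

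**Status.** Protocol 10.5.4.4 says: "Descriptive analysis of the associated symptoms of migraine, nausea, phonophobia and photophobia, will be performed at 2 hours". SAP 3.3 lists the endpoint as exploratory: "Presence of migraine symptoms (nausea, phonophobia, photophobia, vomiting) at all-time points based on first and second dose". SAP 11.7.4 names no test. Unless otherwise stated, SAP 11 tests exploratory efficacy hypotheses "using a logistic regression model with treatment group and background use of medication to reduce the frequency of migraine episodes as covariates".

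**The concern.** Subjects without a given symptom at dosing are to be expected. The diagnostic criteria in Protocol Appendix 2 need only nausea and/or vomiting, or photophobia with phonophobia, and SAP 8.5 provides a category for no baseline symptom. Such a subject can only stay free or develop the symptom, yet is counted with those in whom it resolved.

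The other response endpoints are tied to baseline. Pain-free (SAP 11.2) and headache relief (11.7.5) require pain at dosing, and MBS-free (11.3) requires the symptom to have been present. The by-symptom MBS tables (11.7.3) fill the gap only in part, because they follow the symptom chosen as most bothersome. A subject with nausea who chose photophobia enters no baseline-conditioned nausea result, and vomiting cannot be chosen at all.

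What is at stake is the size and meaning of the reported effects. A percentage labelled as freedom will be read as resolution. Marginal baseline and post-dose percentages cannot be separated into resolution and onset afterwards.

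**Working it through.** **1. The plan's own figure.** Neither document states a figure for the symptom summaries. The stated power for pain-free (above 90%, 570 per arm, one-sided 0.025) was reproduced to check the method. The formula is power = Φ{[|p1 − p0| − z·√(2p̄(1 − p̄)/n)] / √[(p0(1 − p0) + p1(1 − p1))/n]}. With 7.4% on placebo it gives 94.6% (13.9%, 50 mg), 92.8% (13.6%, 100 mg) and 99.99% (18.8%, 200 mg).

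**2. Inputs.** Phase 2 symptom-free rates come from Protocol 10.1 and SAP 2.2.
- Nausea: placebo 59.3%, 200 mg 63.8%.
- Phonophobia: placebo 51.9%, 50 mg 58.2%, 200 mg 59.4%.
- Photophobia: placebo 34.6% (Protocol; the SAP prints 36.4%), 200 mg 58.0%.

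Two things are not given: the pre-dose prevalence π, and whether these rates are among all subjects or only those affected. Both readings are shown, and π and the onset rates are assumptions.

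**3. The identity.** With no new onset, free among all = 1 − π(1 − free among affected). So the difference among all = π × the difference among affected. Presence among all = π(1 − free among affected), so π cancels from the ratio of presence. For nausea, 200 mg, on the affected-subject reading, the ratio is 36.2/40.7 = 0.889 at every π.

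**4. Affected-subject reading, 200 mg v placebo, no onset.**

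| Symptom | Difference, affected | All, π = 0.5 | All, π = 0.8 | Odds ratio, affected → all at π = 0.5 |
|---|---|---|---|---|
| Nausea | 4.5 points | 2.25 | 3.6 | 1.21 → 1.16 |
| Phonophobia | 7.5 | 3.75 | 6.0 | 1.36 → 1.24 |
| Photophobia | 23.4 | 11.7 | 18.7 | 2.61 → 1.83 |

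**5. All-subject reading, nausea 200 mg.** The 4.5-point difference is 4.5/0.5 = 9.0 points among affected subjects at π = 0.5, 6.4 at 0.7 and 5.0 at 0.9.

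**6. Mixing with onset.** Take π = 0.5, nausea on the affected-subject reading, and assumed onset of 3% on placebo and 8% on 200 mg. Presence is 0.5 × 40.7 + 0.5 × 3 = 21.85% on placebo and 0.5 × 36.2 + 0.5 × 8 = 22.1% on 200 mg. The net benefit is −0.25 points, although resolution is 4.5 points better.

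**7. Chance imbalance.** The SD of the between-arm difference in pre-dose presence at π = 0.5 is √(2 × 0.5 × 0.5/570) = 3.0 points.

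**8. Power, if a test were run.** Two-sided 0.05, 570 per arm, 5% onset assumed in both arms, phonophobia 50 mg.
- *All-subject reading*, simulated logistic Wald test: about 57% unadjusted. With pre-dose presence in the model it is about 95% at π = 0.5, 82% at 0.6, 72% at 0.7 and 60% at 0.9.
- *Affected-subject reading*, two-proportion formula, all 570 v affected subjects only: about 23% v 33% at π = 0.5, and 35% v 43% at 0.7.

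**9. Feasibility of the large gains.** On the all-subject reading with 5% onset, placebo resolution = (rate − 0.95(1 − π))/π. For phonophobia at π = 0.5 this is (51.9 − 47.5)/0.5 = 8.8%, close to the lower limit of π = 1 − 51.9/95 = 45%. For photophobia it is −26% at π = 0.5 and −6% at 0.6, so π must exceed 1 − 34.6/95 = 64%.

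**The case against.** The strongest reply is that nothing confirmatory is touched. The summary is exploratory, the protocol calls it descriptive, and SAP 11.7.4 promises only counts and percentages. Where the SAP wants a comparison in a similar section it names one, as it does for disability (11.7.9) and global impression (11.7.12). That stands. A power argument is therefore conditional on someone applying the SAP 11 default model.

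A reader might infer that the plan throws away a large amount of power, for example 57% against 95% for phonophobia 50 mg. The documents do not support that as a general statement. It needs the Phase 2 rates to be all-subject rates and a prevalence near the lowest that those rates allow. At 90% prevalence the gain is about 3 points (57% v 60%).

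A reader might also infer bias. Randomization rules that out for the all-subject comparison. With no new onset the ratio of presence is not diluted either, and SAP 8.5 would let a reader see a baseline imbalance.

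All-subject presence is a legitimate summary in its own right, because it captures symptoms that begin after dosing, which a resolution-only table would miss. That is a reason to keep the table, not to leave it alone. The by-symptom MBS results do condition on baseline, and subjects who name no MBS are assessed on every symptom present (SAP 11.3), but non-chosen symptoms and vomiting remain uncovered.

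**Conclusion.** The point holds as an inexpensive improvement to an exploratory, descriptive summary. SAP 11.7.4 and Protocol 10.5.4.4 count never-affected subjects as free of the symptom and merge resolution with onset. With no new onset, absolute differences shrink by the factor π and odds ratios move towards 1. The factor rests on an assumed prevalence, because the documents give none. Power gains run from small to large and cannot be narrowed without knowing both the prevalence and the Phase 2 denominator.

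It should not be read as a fault in the primary endpoint, the key MBS endpoint, the gatekeeping or the sample size. None of these uses the individual-symptom summaries of SAP 11.7.4.

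**What to change.** 1. Keep the all-subject presence table in SAP 11.7.4.
2. Add, for each of the four symptoms and each time point, resolution among subjects with that symptom pre-dose and, separately, emergence among those without it. For the second-dose tables, use presence at the time of the second dose.
3. State that any treatment comparison of these endpoints under the SAP 11 logistic model includes pre-dose presence of that symptom as a covariate.
4. Align Protocol 10.5.4.4 so that freedom from a symptom requires it to have been present pre-dose.

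The cost is SAP and protocol wording and some extra table columns; no new data are needed. The drawback is smaller denominators in the added tables (at an assumed 50% prevalence, about 0.5 × 570 = 285 per arm). The existing table stays beside them.

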11.7.5 Headache Relief

Counts and percentages of the number of subjects with headache relief will be presented at the 0.5, 1, 1.5, 2, 3, 4, 24, and 48-hour post-dose time points. This summary will be presented by treatment group for the ITT population, based on first dose.

Headache relief is defined as experiencing a moderate (2) or severe (3) headache at baseline which becomes mild (1) or none (0) at the summarized time point, or a mild headache at baseline which becomes none at the summarized time point.

Subjects missing a headache severity at baseline or at the summarized time point will not be summarized at that time point.

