## **10.7 Missing Values**

The primary and key secondary endpoints are defined as proportions. If a subject has a missing value for a proportion endpoint, the subject will be classified as a nonresponder for this endpoint. Subjects who have more than one symptom (nausea, phonophobia or photophobia) but do not select one as the MBS prior to dosing, will be considered inevaluable for the MBS endpoint as there is no MBS selected to evaluate. In the case of subjects that have only one symptom (nausea, phonophobia, or photophobia) at predose but do not select a MBS, the one symptom will be considered the MBS for analysis.

For subjects who do not record a symptom rating, that symptom (pain, photophobia, phonophobia or nausea) will be assumed to be present at all time points where data are missing. Subjects who do not provide a headache severity rating at baseline will be assumed to have all four symptoms (pain, nausea, photophobia and phonophobia) at all time points. If recurrence medication is taken within 24 hours post dosing, or from 24 hours to 48 hours post dosing, even if no headache is reported, headache recurrence will be assumed for the first dose analysis.

The sensitivity analysis for handling missing data is described in detail in the SAP.

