 - The time intervals are 30 minutes, 1 hour, 1.5 hours, 2 hours, 3 hours, 4 hours, 24 hours, and 48 hours after the first dose of study medication. The e-diary sets the post dose assessments based on the recorded time of dosing. A subject that begins reporting their migraine at the exact time of dosing will have all of the post dose assessment time points available to them. If a subject starts recording their information in the e-diary after they dose including the time of dosing, the assessments that become available for them are based on the time of dosing, relative to when they accessed the e-diary. For example, if at 1-hour post actual dosing the subject initiates migraine mode and begins entering data into the e-diary, the subject will be allowed to respond to the initial questions about their migraine and time of dosing and then based on the time they record for dosing they automatically will miss subsequent time points, i.e.; the 30 minute and 1-hour time points. A missed time point is missed.
 - Alarms occur at the predefined time points to remind the subject it is time to complete the assessments. The Migraine Questions button is always available, but the subject is not be able to answer the questions until prompted by an alarm within a study migraine.
- Migraine Mode – Second Dose (Optional)
 - The subject should only take a second dose of study medication if the migraine pain is not gone by two hours after the first dose or the migraine pain was gone and came back two hours or more after the first dose (up to 24 hours after first dose).
 - The Dose 2 button will appear AFTER the e-diary recognizes 2 hours have passed since the first dose and remains until the 24-hour time point.
 - During the 2-hour post dose assessment the subject will be asked to indicate if he/she would like to take a second dose of study medication
 - If a second dose is reported alarm intervals are the same as for the reporting of the first dose and any remaining alarms from the first dose are cancelled. However, if

the subject inadvertently enters a dosing time of the second dose occurring prior to the first dose the first dose alarms do not stop and subject can therefore response to post-dose assessments based on time of dosing of first dose, therefore not really assessing their response to the second dose.

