5.2 Analysis of First and Second Doses

Any analyses based on first dose will only include data observed up to the time of dosing with a second dose. These summaries will be presented based on the first dose taken. The exception to this is the primary and secondary endpoints at the 2-hour time point; if a second dose is taken before the 2-hour time point, the subject will still be included in the summary at 2 hours and will be analysed as having not achieved headache pain-free or MBS-free status at 2 hours.

Any analyses based on the second dose will only include data observed on or after the time of dosing with a second dose. These summaries will be presented by treatment sequence, listed in Section 2.3. Analyses based on the second dose will be done for both the rescue and recurrence subpopulations.

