11.7.6 Time to Headache Pain-Free

The time to headache pain-free will be presented by treatment group using a Kaplan-Meier analysis. This summary will be presented for the ITT population, based on the first dose.

The number of subjects experiencing headache pain-free, and the number of subjects censored, will be summarized. The Kaplan-Meier estimates, and 95% confidence intervals calculated using the log-log transformation, of the number of hours for 25%, 50%, and 75% of subjects to experience headache pain-free will be presented. The Kaplan-Meier estimate, and 95% confidence interval, of the probability of experiencing headache pain-free will be presented at the 0.5, 1, 1.5, 2, 3, 4, and 24-hour post-dose time points.

Time to headache pain-free will be calculated as:

date/time headache severity is reported as none (0) –
date/time of dosing of mild (1), moderate (2), or severe (3) headache

Subjects who do not report a headache with severity of none, or who report a headache with a severity of none after 24 hours post-dose, will be censored at the time of their last non-missing post-dose headache severity assessment at or before 24 hours. Subjects with missing baseline headache severity, or who report a headache severity of none (0) at baseline, will be censored at the time of first dose.

A figure of the Kaplan-Meier analysis will also be presented.

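### Exploratory first-dose rates and time-to-event curves drop or censor subjects when they take a second dose or stop recording, so later results describe an outcome-selected subset, with unknown bias between arms

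*SAP*

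**What the plan says.** **Cut-off.** SAP 5.2: "Any analyses based on first dose will only include data observed up to the time of dosing with a second dose". It makes one exemption: "The exception to this is the primary and secondary endpoints at the 2-hour time point", where an early second dose counts as not pain-free and not MBS-free. SAP 5 adds that once a second dose is reported in the diary, "any remaining alarms from the first dose are cancelled".

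**Rate tables.** SAP 11.7.5, which covers 0.5 to 48 hours including 2 hours: "Subjects missing a headache severity at baseline or at the summarized time point will not be summarized at that time point". SAP 11.7.3, for MBS-free: "Subjects missing symptoms at baseline or at the summarized time point will not be summarized at that time point". SAP 11.7.1, for pain-free, goes the other way: "Subjects missing a severity assessment at a post-dose time point will not be counted as pain-free".

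**Curves.** In SAP 11.7.6 a subject with no event "will be censored at the time of their last non-missing post-dose headache severity assessment at or before 24 hours". SAP 11.7.7 and 11.7.8 use the same rule for relief and MBS-free.

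**Who takes a second dose.** SAP 4.1 defines rescue use as a second dose in a subject not pain-free at 2 hours, and recurrence use as a second dose after pain has come back in a subject who was pain-free at 2 hours.

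**Protocol.** Section 10.7: "For subjects who do not record a symptom rating, that symptom (pain, photophobia, phonophobia or nausea) will be assumed to be present" wherever data are missing. Section 10.5.1 treats a subject with no 2-hour severity, or with rescue inside 2 hours, as having no headache response in both the ITT and mITT analyses. The synopsis defines headache response as moderate or severe pain falling to mild or none, which is what the SAP calls relief. SAP 5.1, the list of changes from the protocol, does not mention this one.

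**The concern.** The protocol's secondary objective is to explore the time course of the first dose on pain and the MBS. The 11.7.3 and 11.7.5 tables and the 11.7.6 to 11.7.8 curves are much of the evidence for it, and SAP 11 applies two-sided 0.05 tests to exploratory endpoints.

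A second dose is not a random reason for having no value. It follows inadequate response at 2 hours or a return of pain. Leaving these subjects out of the denominator, or censoring them as if their future matched that of subjects who needed nothing more, makes inclusion depend on the outcome. The reported 24-hour relief rate then answers a narrower question (relief among those who took no second dose and kept recording), although the table is labelled as ITT by first dose.

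The opposite gap exists for other rescue medication. Protocol 7.3.1 permits some of it after the 2-hour assessments. The SAP 5.2 cut-off applies only to a second dose of study drug, so a response after another rescue drug can be credited to the first dose.

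**Working it through.** **1. Follow two subjects through the rules.**

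- *Subject A*: moderate at baseline, mild at 2 hours, second dose soon after. Relief at 2 hours: counted. Relief at 3, 4, 24 and 48 hours: omitted. Time to relief: an event. Time to pain-free: censored at the last first-dose assessment. Pain-free at 3 hours under 11.7.1: in the table, not pain-free.
- *Subject B*: severe at 2 hours, takes a permitted non-study rescue drug, no pain at 4 hours. Nothing in 11.7.5 to 11.7.7 stops this counting as first-dose relief and as a first-dose event.

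**2. Figures in the documents.** None is given for second-dose use, other rescue or missing data by arm. The nearest stated figure is power above 90% for 2-hour pain-free with 570 per arm at one-sided 0.025. It reproduces (94.6%, 92.8% and above 99.9% for 50, 100 and 200 mg) but concerns the primary endpoint. On the same planning rates, 1 − 0.074 = 92.6% of placebo and 1 − 0.188 = 81.2% of 200 mg subjects are not pain-free at 2 hours. That is eligibility for rescue, not uptake. Everything below rests on assumed uptake.

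**3. Denominator effect.** Let u be the share of the arm taking a second dose and r the relief rate among the rest. The SAP reports r. Counting second-dose takers as non-responders gives (1 − u)r.

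- u = 55% placebo, 35% on 200 mg, r = 85% in both: SAP 85% v 85%; alternative 0.45 × 0.85 = 38% v 0.65 × 0.85 = 55%, a 17-point difference.
- A 15-point gap in use (40% v 25%, or 60% v 45%): the difference shifts by 0.15 × 0.70 = 10.5 to 0.15 × 0.85 = 12.8 points for r of 70% to 85%.

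The zero difference under the SAP is an input here, because r was set equal in both arms.

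**4. Direction of bias.** Let p be the true response rate and q the share of non-responders removed, assuming no responders are removed. The reported rate is p / [p + (1 − p)(1 − q)], so the reported odds ratio equals the true one × (1 − q placebo) / (1 − q active). Phase 2 photophobia-free rates serve as a stand-in for MBS-free: 34.6% placebo (protocol 10.1) and 58.0% on 200 mg, odds ratio 2.61.

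| q placebo / 200 mg | Reported rates | Odds ratio |
|---|---|---|
| 20% / 20% | 39.8% v 63.3% | 2.61 |
| 60% / 60% | 56.9% v 77.5% | 2.61 |
| 60% / 40% | 56.9% v 69.7% | 1.74 |
| 30% / 40% | 43.0% v 69.7% | 3.05 |

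SAP 2.2 gives the placebo rate as 36.4%. The odds ratios are then 2.41, 2.41, 1.61 and 2.82, with the same pattern.

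**5. Curves.** Take pain-free by 24 hours, 2-hour rates p2 of 7.4% and 18.8%, and an assumed share e = 50% of those still followed becoming pain-free later. Here q is the share of 2-hour non-responders who take a second dose. Censoring gives p2 + (1 − p2)e = 53.7% v 59.4%, difference 5.7 points. Treating a second dose as ending the chance of a first-dose response gives p2 + (1 − p2)(1 − q)e:

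- q = 20% in both arms: 44.4% v 51.3%.
- q = 60% in both arms: 25.9% v 35.0%.
- q = 60% v 40%: 25.9% v 43.2%, difference 17.2 points.
- q = 30% v 40%: 0.074 + 0.926 × 0.7 × 0.5 = 39.8% v 0.188 + 0.812 × 0.6 × 0.5 = 43.2%, difference about 3.4 points.

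Censoring raises both arms in every case. Compared with 5.7, it understates the difference in the third case and overstates it in the fourth.

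**The case against.** Several points on the other side stand.

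- **Scope.** These endpoints are listed as exploratory in SAP 3.3 and lie outside the testing sequence in 11.1. At 2 hours the primary and key secondary analyses keep early second-dose takers and missing subjects as non-responders.
- **Partial visibility.** Pain-free tables keep missing subjects, sustained pain-free (11.7.2) bars later medication, 11.7.10 tabulates rescue and recurrence use by group, and numbers censored are reported. A careful reader could see part of the problem, but could not correct the relief and MBS tables from this.
- **Choice of estimand.** Counting rescue as failure is one reasonable choice among several, and protocol 10.7 concerns unrecorded ratings, not second doses as such.

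Three stronger readings are tempting and are not supported.

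- *Placebo is inflated most, so the drug effect is hidden.* More placebo subjects are eligible for rescue on planning rates, but no uptake by arm is given. SAP 11.5 raises heavier missingness on placebo only as a possibility, and only for 2-hour data. Equal uptake among non-responders leaves the odds ratio unchanged, and unequal uptake moves it either way.
- *Everyone removed is a non-responder.* A rescue taker may have mild pain, hence relief, or be MBS-free. A recurrence taker was pain-free at 2 hours. In the curves, anyone with the event before the second dose is already counted.
- *SAP 11.7.3 and 11.7.5 contradict 11.7.1.* SAP 5.3 treats missing as missing unless a section says otherwise, and 11.7.1 says otherwise for a different endpoint. The result is different denominators at the same hour, not a contradiction.

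**Conclusion.** The point holds for the exploratory first-dose analyses only. Removal from the relief and MBS-free tables, and censoring in the three curves, depend on outcome. Responses after other rescue medication can be credited to the first dose. Rates after 2 hours will therefore tend to be too high as estimates of first-dose response. The 2-hour relief table is also affected, because relief is outside the SAP 5.2 exemption.

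The size cannot be fixed from the documents. Under the stated assumptions the difference between arms shifts by 10.5 to 12.8 points for a 15-point gap in second-dose use, and by 17 points for a 20-point gap with 85% relief. These are illustrations, and the sign of the bias in the comparison is unknown.

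For missing values there is a departure from protocol 10.7, and for 2-hour relief from protocol 10.5.1, that SAP 5.1 does not list. No confirmatory conclusion is at risk. The change is worth making because these analyses serve the stated secondary objective.

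**What to change.** - **SAP 11.7.3 and 11.7.5:** use as denominator all subjects in the summarized population with the headache or symptom at baseline. Count a missing value, a second dose, or other rescue before the time point as non-response. This extends the rule that the SAP already applies to its main endpoints at 2 hours.
- **SAP 11.7.6 to 11.7.8:** treat a second dose or other rescue before the event as a competing event and report cumulative incidence to 24 hours. Subjects who only stop recording may still be censored. Carrying rescue takers as event-free to 24 hours gives the same answer only when there is no such other censoring. SAP 11.7.10 already uses the diary question on other medication.
- **Reporting:** show numbers with a second dose, other rescue and missing data by arm and time point. Keep the current versions as supplementary.
- **SAP 5.1:** list any remaining departure from protocol 10.7 and 10.5.1.

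The cost is SAP wording and programming. Reported later rates will be lower, and some subjects with partial benefit who took a second dose will count as non-responders; the supplementary tables let a reader see how much that matters.
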